8.5 SAFETY REPORTING CRITERIA TO THE PHARMACEUTICAL COLLABORATORS

Reporting will be per the collaborative agreement.

8.6 REPORTING PREGNANCY

All required pregnancy reports/follow-up to OSRO will be submitted to: [contact] and to the CCR PI and study coordinator. Forms and instructions can be found here: <https://ccrod.cancer.gov/confluence/display/CCRCRO/Forms+and+Instructions>.

8.6.1 Maternal exposure

If a patient becomes pregnant during the course of the study, the study treatment should be discontinued immediately, and the pregnancy reported to the Sponsor no later than 24 hours after the Investigator becomes aware of it.

Pregnancy itself is not regarded as an SAE. However, congenital abnormalities or birth defects and spontaneous miscarriages that meet serious criteria (section **8.1.2**) should be reported as SAEs.

The outcome of all pregnancies (spontaneous miscarriage, elective termination, ectopic pregnancy, normal birth, or congenital abnormality) should be followed up and documented.

8.6.2 Paternal exposure

Male patients should refrain from fathering a child or donating sperm during the study and for 120 days after the last dose of study drug.

Pregnancy of the patient's partner is not considered to be an AE. However, the outcome of all pregnancies (spontaneous miscarriage, elective termination, ectopic pregnancy, normal birth, or congenital abnormality) occurring from the date of the first dose until 120 days after the last dose should, if possible, be followed up and documented.

8.7 REGULATORY REPORTING FOR STUDIES CONDUCTED UNDER CCR-SPONSORED IND

Following notification from the investigator, CCR, the IND sponsor, will report any suspected adverse reaction that is both serious and unexpected. CCR will report an AE as a suspected adverse

reaction only if there is evidence to suggest a causal relationship between the study product and the adverse event. CCR will notify FDA and all participating investigators (i.e., all investigators to whom the sponsor is providing drug under its INDs or under any investigator's IND) in an IND safety report of potential serious risks from clinical trials or any other source, as soon as possible, in accordance with 21 CFR Part 312.32.

All serious events will be reported to the FDA at least annually in a summary format.

8.8 SPONSOR PROTOCOL NON-ADHERENCE REPORTING

Protocol non-adherence is defined as any noncompliance with the clinical trial protocol, GCP, or protocol-specific procedural requirements on the part of the participant, the Investigator, or the study site staff inclusive of site personnel performing procedures or providing services in support of the clinical trial.

It is the responsibility of the study Staff to document any protocol non-adherence identified by the Staff or the site Monitor on the OSRO Site Protocol Non-Adherence Log. The protocol-specific, cumulative non-adherence log should be maintained in the site essential documents file and submitted to OSRO via [contact] on the **first business day of each month over the duration of the study**. In addition, any non-adherence to the protocol should be documented in the participant's source records and reported to the local IRB per their guidelines. OSRO required protocol non-adherence reporting is consistent with E6(R2) GCP: Integrated Addendum to ICH E6(R1): 4.5 Compliance with Protocol; 5.18.3 (a), and 5.20 Noncompliance; and ICH E3 16.2.2 Protocol deviations.

9 CLINICAL MONITORING

Clinical site monitoring is conducted to ensure that the rights of the participants are protected, that the study is implemented per the approved protocol, Good Clinical Practice and standard operating procedures, and that the quality and integrity of study data and data collection methods are maintained. Monitoring for this study will be performed by NCI CCR Office of Sponsor and Regulatory Oversight (OSRO) Monitoring based on OSRO standards, FDA Guidance E6(R2) Good Clinical Practice: Integrated Addendum to ICH E6(R1) March 2018, and applicable regulatory requirements.

Details of clinical site monitoring will be documented in a Clinical Monitoring Plan (CMP) developed by OSRO. CMPs will be protocol-specific, risk-based and tailored to address human subject protections and integrity of the study data. The intensity and frequency of monitoring will be based on several factors, including study type, phase, risk, complexity, expected enrollment rate, and any unique attributes of the study and the site. OSRO Monitoring visits and related activities will be conducted throughout the life cycle of each protocol, with the first activity being before study start to conduct a Site Assessment Visit (SAV) (as warranted), followed by a Site Initiation Visit (SIV), Interim Monitoring Visit(s) (IMVs), and a study Close-Out Visit (COV).

Some monitoring activities may be performed remotely, while others will take place at the study site(s). Monitoring visit reports will describe visit activities, observations, findings of protocol non-adherence and associated action items or follow-up required for resolution of findings. Monitoring reports will be distributed to the study PI, NCI CCR QA, coordinating center (if applicable) and the OSRO regulatory file.

If protocol non-adherence is identified by the Monitor (i.e., any noncompliance with the clinical trial protocol, GCP, or protocol-specific procedural requirements on the part of the participant, the

Investigator, or the site Staff) the Monitor will note the observation, review with site Staff and if unresolved, request that the Staff document the non-adherence on the protocol-specific OSRO Site Protocol Non-Adherence Log (see Section 8.8).

10 STATISTICAL CONSIDERATIONS

10.1 STATISTICAL HYPOTHESIS

10.1.1 Primary endpoints:

- To determine the safety and tolerability and the recommended phase 2 dose (RP2D) of M7824 and M9241 in combination with SBRT as neoadjuvant / perioperative treatment in subjects with pancreas cancer:
 - number, severity, and duration of treatment-related AEs for the combination treatment of M7824 and M9241 administered in combination with a 5-day course of SBRT according to CTCAE v5.0
 - rate of completion of neoadjuvant SBRT courses when given with M7824 and M9241.
- To determine a preliminary estimate of efficacy as best overall response (BOR) according to RECIST 1.1 of M7824 and M9241 in combination with SBRT as neoadjuvant / perioperative treatment in subjects with locally advanced pancreas cancer will be measured by
 - Best Overall Response (BOR) according to RECIST 1.1

10.1.2 Secondary endpoints

- Overall survival in patients after completion of SBRT in combination with M9241 and M7824.
- Progression-free survival of all patients and PFS of patients who did not undergo surgical resection (expressed as median PFS).
- Fraction of patients with LAPC who can undergo surgical resection after M7824 and M9241 in combination with SBRT treatment.
- Time-to-recurrence in patients who underwent surgical resection will be measured as time from surgical resection to disease recurrence (expressed in months).
- Rate of complete pathologic response will be measured as fraction of patients who had a complete pathologic response of all patients who underwent surgery.

10.2 SAMPLE SIZE DETERMINATION

Phase I:

The investigational agents M7824 and M9241 will be first tested in combination for safety and tolerability prior to assessing both in combination with SBRT. The safety phase IA run-in of M7824 and M9241 will accrue either pancreatic cancer patients with locally advanced surgically unresectable disease or patients with stage IV disease.

Dose Level 0 of 1,200 mg for M7824 every 2 weeks will be tested in combination with 16.8µg/kg of M9241 every four weeks will be first given to 6 patients as a safety run-in. If there are 0-1

DLTs, the study will proceed to the phase IB of M7824 and M9241 in combination with SBRT starting with DL0.

If there are ≥ 2 DLTs at DL0, 6 patients will be enrolled at DL -1 (1,200 mg M7824 q2 weeks and 12 μ g/kg every 4 weeks). If 6 patients at the DL-1 have 0-1 DLTs, DL-1 will be combined with SBRT and the study will move to phase IB. If 2 or more DLTs are seen at the DL-1, there will be no further attempts of combining M7824 with M9241 and neither the M7824 and M9241 in combination with SBRT phase IB or the phase II part will be carried out. The first safety run-in of M7824 in combination with M9241 might have a minimum of 6 and a maximum of 12 patients.

The safe dose of M7824 and M9241 will then be given in combination with a 5-day course of SBRT. Estimated during phase IA DL of M7824 and M9241 will be given to 6 patients. If there are 0-1 DLTs in the first 6 subjects, the dose of M7824 and M9241 will be used as the recommended phase 2 dose and the study will proceed to the phase II part. If there are ≥ 2 DLTs in the initial combination with SBRT, there will be a dose reduction of M9241 (if recommended dose was 16.8 μ g/kg, M9241 will be reduced to 12 μ g/kg, if the safe dose of M9241 when combined with M7824 in the phase IA part was 12.0 μ g/kg, the dose will be reduced to 8.0 μ g/kg). If there are 0-1 DLTs in the first 6 subjects, this dose of M7824 and M9241 will be used as the recommended phase 2 dose and the study will proceed to the phase II part. If there are ≥ 2 DLTs in 6 patients treated with the reduced M7824 levels in combination with SBRT, no further attempts will be made to combine M7824 and M9241 with SBRT and the study will not proceed to the phase II part. The second safety run-in of M7824 and M9241 in combination with SBRT might have a minimum of 6 and a maximum of 12 patients.

Following determination of safe doses of M7824 and M9241 when combined with SBRT the study may proceed to the phase II part. Thus, a minimum of 12 and a maximum of 24 evaluable patients will be enrolled in the phase I cohorts.

Phase II:

The study will be conducted using a Simon two-stage phase 2 minimax design. The objective of the trial will be to determine whether this novel combination of M7824 and M9241 in combination with SBRT can be associated with a response rate (PR + CR; RECIST) that can rule out 10% ($p_0=0.10$) in favor of an improved response rate of 30% ($p_1=0.30$). Using $\alpha=0.10$ (probability of accepting a poor agent) and $\beta=0.10$ (probability of rejecting a good agent), initially 16 evaluable patients will be enrolled into the phase II study, including up to 6 patients from the completed safety cohort Phase IB of M7824 and M9241 in combination with SBRT if they are completely eligible for the phase II portion of the trial. If 0 to 1 of 16 patients respond, then no further patients will be enrolled. If 2 or more of the first 16 evaluable patients enrolled have a response (PR or CR), then accrual will continue until a total of 25 evaluable patients have been enrolled. If 2 to 4 of the 25 has a clinical response, then this will be considered inadequate for further investigation of this regimen. If 5 or more of 25 (20%) respond, then this will warrant further investigation in a subsequent trial. Under the null hypothesis (10% response rate), the probability of early termination is 51.5%.

Thus, with up to 24 participants in the phase I cohort and up to 25 evaluable participants in phase II, the trial may require up to 49 participants to be treated. This number may be reduced by up to 6 patients if there are < 2 DLTs in the second safety run-in of M7824 and M9241 in combination with SBRT and those patients are included in phase II. To allow for a small number of inevaluable

patients, the accrual ceiling will be set at 52 participants. With an anticipated accrual rate of 10 patients per year, it is expected that the trial may complete accrual within 5 years.

10.3 POPULATIONS FOR ANALYSIS

Evaluable for overall response: all patients who receive at least one dose of M7824 and M9241 in combination with SBRT at the dose level determined to be safe in the safety run-in Phase IB of M7824 and M9241 in combination with SBRT will be included in the statistical analyses performed.

Evaluable for toxicity: All patients will be evaluable for toxicity from the time of their first treatment with M7824 and M9241 in combination with SBRT.

Evaluable for MTD: Subjects enrolled to the safety run-in portion of the study are evaluable. However, subjects who do not complete the DLT observation period for reasons other than a DLT will be replaced and not included in the evaluation.

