3.1.1 Dose Limiting Toxicity

The DLT period for the phase IA is 6 weeks (Day -14 to Day 28 of Cycle 1), the DLT period for the phase IB is 4 weeks (from Day 1 Cycle 1 to Day 28 Cycle 1).

Any Grade ≥ 3 adverse event (AE), occurring during the DLT evaluation period, **except** for those listed below:

- Adverse event unrelated, or unlikely related to study agents AND probably or definitely related to other causes
- Grade 3 or 4 clinically asymptomatic neutropenia if not lasting > 1 cycle (14 days) (observed on laboratory value only)
- Clinically asymptomatic grade 3 thrombocytopenia if not lasting > 1 cycle (14 days) (observed on laboratory value only with no clinically discernable bleeding events)
- Grade 3 diarrhea or skin toxicity that resolves to Grade ≤ 1 in less than 7 days after medical management (e.g., immunosuppressant treatment) has been initiated
- Tumor flare phenomenon defined as local pain, irritation, or rash localized at sites of known or suspected tumor.
- Transient (≤ 6 hours) Grade 3 flu-like symptoms or fever, which is controlled with medical management.
- Transient (≤ 24 hours) Grade 3 fatigue, local reactions, headache, nausea, emesis that resolves to \leq Grade 1 or Baseline grade.

- Any isolated and single Grade 3 liver function test abnormality in the form of transaminase, alkaline phosphatase, or bilirubin elevation with NO other associated laboratory (or other) abnormality that is not associated with symptoms or clinical manifestations of hepatitis or any immune-related event and which has resolved to Grade ≤ 1 within the subsequent cycle (14 days)
- Any isolated and single Grade 3 amylase or lipase abnormality with no other associated laboratory (or other) abnormality that is not associated with symptoms or clinical manifestations of pancreatitis and which has resolved to Grade ≤ 1 within the subsequent cycle (14 days)
- Any isolated and single Grade 3 Hgb decrease (< 8.0 g/dL) that is clinically manageable with blood transfusions or erythroid growth factor and has resolved to Grade 2 not requiring blood transfusions or erythroid growth factor therapy with the subsequent cycle (14 days).

Failure to resume SBRT after a hold of ≥ 1 week will be analyzed as a DLT within respective dose level group (Phase IB only)

3.1.2 Phase IA/IB:

Every subject of each dose level group of the phase 1 study will be observed for at least 7 days after first dose of M7824 or M7824 and M9241 before the subsequent subject can be treated.

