6 DATA COLLECTION AND EVALUATION

6.1 DATA COLLECTION

The PI will be responsible for overseeing entry of data into an in-house password protected electronic system (C3D) and Labmatrix ensuring data accuracy, consistency and timeliness. The principal investigator, associate investigators/research nurses and/or data manager will assist with the data management efforts. Primary and final analyzed data will have identifiers so that research data can be attributed to an individual human subject participant.

All adverse events, including clinically significant abnormal findings on laboratory evaluations, regardless of severity, will be followed until return to baseline or stabilization of event.

Document AEs from the administration of the first study intervention through 28 days after the last study agent (s) is administered. Beyond 28 days after the last intervention, only adverse events which are serious and related to the study intervention need to be recorded.

An abnormal laboratory value will be recorded in the database as an AE only if the laboratory abnormality is characterized by any of the following:

- Results in discontinuation from the study
- Is associated with clinical signs or symptoms
- Requires treatment or any other therapeutic intervention
- Is associated with death or another serious adverse event, including hospitalization.
- Is judged by the Investigator to be of significant clinical impact

- If any abnormal laboratory result is considered clinically significant, the investigator will provide details about the action taken with respect to the test drug and about the patient's outcome.

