10.4.2 Analysis of the primary endpoints

For the patients in the dose de-escalation portion, the safety and tolerability and the recommended phase 2 dose (RP2D) of M7824 and M9241 in combination with SBRT as neoadjuvant / perioperative treatment in subjects with pancreas cancer will be evaluated by reporting the number, severity, and duration of treatment-related AEs for the combination treatment of M7824 and M9241 administered in combination with a 5-day course of SBRT according to CTCAE v5.0 . The rate of completion of neoadjuvant SBRT courses when given with M7824 and M9241 will be reported as well using descriptive statistics.

Patients who are in the efficacy evaluation will have the fraction objective responses measured by RECIST1.1 determined by dividing the number of patients with an objective response by the number of evaluable patients who are treated at the MTD and reported along with two sided 80% and 95% confidence intervals.

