10.4.4 Safety analyses

Patients in the phase I portion of the trial will be assessed for toxicity by reporting the grades of toxicity and the type of toxicity observed for all patients. Patients will be enrolled and evaluated in the phase I cohorts of the trial as described in the phase I sample size determination section. Patients will continue to be enrolled onto the phase II cohort if the cumulative fraction of patients with greater or equal grade 3 DLT is less than 1/3.

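### Section 10.3's toxicity population conflicts with other sections, and no adverse event summary is planned for the Phase II patients treated at the RP2D

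*Combined protocol and SAP*

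**What the plan says.** **Who is in the toxicity set, and from when.** Section 10.3 says: "All patients will be evaluable for toxicity from the time of their first treatment with M7824 and M9241 in combination with SBRT". For the MTD evaluation the same section is wider: "Subjects enrolled to the safety run-in portion of the study are evaluable". Section 3.1.1 opens the DLT windows before any radiation: "The DLT period for the phase IA is 6 weeks (Day -14 to Day 28 of Cycle 1", and for Phase IB on Day 1 of Cycle 1. Section 6.1 collects from the start: "Document AEs from the administration of the first study intervention through 28 days after the last study agent". Section 10.4.6 assesses toxicity in each phase I group of 6 and names the two-drug cohort that has no SBRT.

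**What is reported.** The primary safety endpoint in 10.1.1 is the "number, severity, and duration of treatment-related AEs for the combination treatment of M7824 and M9241 administered in combination with a 5-day course of SBRT", together with the SBRT completion rate. It carries no phase limit. The analysis in 10.4.2 begins: "For the patients in the dose de-escalation portion, the safety and tolerability and the recommended phase 2 dose (RP2D". The SBRT completion rate follows in the same paragraph. Section 10.4.4 begins: "Patients in the phase I portion of the trial will be assessed for toxicity by reporting the grades of toxicity and the type of toxicity", and extends this to all patients in that portion. It ends with a rule that Phase II enrolment continues while the cumulative DLT fraction is below 1/3.

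**The concern.** There are two separate defects.

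First, the population sentence in 10.3 does not match the treatment schedule. Cohort 1 never receives SBRT. In Cohorts 2 and 3 the drugs start on Day 1 and SBRT on Day 17 (+5 days). A programmer who applies 10.3 as written would exclude Cohort 1, the early drug period, and anyone who stops before radiation, possibly because of toxicity.

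Second, both sentences that plan AE reporting stop at the de-escalation or phase I portion. Most patients treated at the RP2D will be in Phase II, and no sentence plans an AE summary for them.

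Safety of the regimen is the first primary objective. Section 1.2.5 says that no clinical data exist for the two drugs together, and 1.2.9.1 says that the side effect profile with SBRT is unknown. What is at stake is the precision and completeness of the reported safety result at the dose the trial recommends.

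**Working it through.** **1. The plan's own counts (3.1.2.1, 3.1.2.2, 10.2).** Phase I maximum: 12 + 12 = 24. Trial maximum: 24 + 25 = 49, or 49 − 6 = 43 if 6 Phase IB patients count in Phase II. Both agree with 10.2. The stated probability of early termination also reproduces: P(X ≤ 1 | n = 16, p = 0.10) = 0.90^16 + 16 × 0.10 × 0.90^15 = 0.185 + 0.329 = 0.515.

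**2. The 10.3 start point against the other sections.**

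| Patients or time | 10.3 read literally | Other text |
|---|---|---|
| Cohort 1, 6 to 12 patients, no SBRT | No evaluable time | DLTs from Day −14 (3.1.1); evaluable for MTD (10.3); inside the phase I report (10.4.4); assessed per group of 6 (10.4.6) |
| Cohorts 2 and 3, Day 1 to SBRT start | Not evaluable for 17 − 1 = 16 to 22 − 1 = 21 days | Cohort 2 DLTs count from Day 1 (3.1.1); AEs documented from first intervention (6.1) |
| Cohorts 2 and 3, stopped before SBRT | Never evaluable | AEs documented (6.1); a DLT in Cohort 2 still counts (3.1.1) |

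The pre-SBRT period is 16/28 = 57% to 21/28 = 75% of Cycle 1. In the third row, a Cohort 2 patient who stops early without a DLT is replaced for the MTD evaluation. The toxicity set is then the only safety set left for that patient's AEs.

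**3. Patients without a planned AE summary.** Phase IB tests levels of 6, so 6 phase I patients are treated at the RP2D with SBRT. Section 3.1.3 counts them within the 25.

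- All 6 count and the trial reaches stage 2: 25 − 6 = 19 Phase II patients. That is 19/25 = 76% of patients at the RP2D.
- As a share of all treated patients: 19/(6 + 6 + 19) = 19/31 = 61% on the shortest path, and 19/(12 + 12 + 19) = 19/43 = 44% on the longest.
- Only k of the 6 are fully eligible, as 10.2 allows: 25 − k, so 19 to 25.
- Stop at stage 1 with all 6 counted: 16 − 6 = 10.

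**4. Precision of the reported RP2D set.** If no event of a given type is seen in n patients, the one-sided 95% upper limit on its rate is 1 − 0.05^(1/n).

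- n = 6: 1 − 0.05^(1/6) = 39%
- n = 16 (stop at stage 1): 1 − 0.05^(1/16) = 17%
- n = 25: 1 − 0.05^(1/25) = 11%

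The exact two-sided 95% upper limits for n = 6 and n = 25 are 46% and 14%.

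**The case against.** The strongest reply is that the rest of the document supplies what 10.3 and 10.4 word badly.

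- **Cohort 1.** Section 10.4.4 reports toxicity for all phase I patients and 10.4.6 names the cohort without SBRT. Its DLTs set the dose carried into Phase IB. This stands: a reader might infer from 10.3 alone that Cohort 1 is lost from the safety results, but the documents do not support that. What remains is a contradiction between sections.
- **Pre-SBRT events.** The phrase naming both drugs in combination with SBRT is used throughout as a label for the regimen, so first treatment could mean Day 1. Phase IB DLTs count from Day 1 and so enter the RP2D decision. This stands as a possible reading. A population definition should not depend on it, and even that reading does not fit Cohort 1.
- **Phase II.** AEs are collected (6.1), reviewed for each patient (7.4.1), subject to the halting rules in 3.2, and covered by the cumulative DLT rule in 10.4.4. A reader might infer that Phase II toxicity goes unwatched; that is not so. But monitoring is not a planned summary, and 3.1.1 defines DLT windows only for Phases IA and IB. Nor are the phase limits obvious shorthand: 10.4.5 names both phases when it means both.
- **SBRT completion rate.** Its sentence in 10.4.2 does not itself repeat the restriction. The limit is inferred from the sentence before it, so this part is less certain than the AE part.

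**Conclusion.** The point holds as two findings.

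1. The toxicity start point in 10.3 conflicts with 3.1.1, 6.1, 10.4.4 and 10.4.6, and the passages must be reconciled. Whether data would actually drop out depends on which sentence is followed.
2. No AE summary is planned for Phase II patients treated at the RP2D: 19 if all 6 run-in patients count toward the 25, more if some do not, about 10 if the trial stops at stage 1. The reported RP2D safety result would rest on 6 patients instead of up to 25, with zero-event upper limits of 39% and 11%.

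These figures describe the precision of what is reported, not whether events are noticed. One could compute that an event with an assumed true rate of 10% is absent from 6 patients with probability 0.90^6 = 53%, and from 25 with 0.90^25 = 7%, and infer that such events would be missed. The documents do not support that inference, because Phase II AEs are recorded; the 10% rate is also not theirs.

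The sponsor should make the change: as written, the plan limits a primary safety result to a minority of the patients treated at the recommended dose.

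**What to change.** In 10.3, define the toxicity set as all patients who receive at least one dose of M7824 or M9241, from the first dose of either agent (Day −14 in Phase IA, Day 1 otherwise).

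In 10.4.2 and 10.4.4, report AEs for all treated patients by cohort and dose level. Add one pooled report of AEs and the SBRT completion rate for all patients treated at the RP2D with SBRT, Phase IB and Phase II together. A split by onset before or after the first SBRT fraction is optional.

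The cost is SAP wording and a few more tables from data that 6.1 already collects. No extra visits or patients are needed, and clinical management does not change.
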